Each study participant will receive a notification letter and will be asked to schedule a BD-1 visit at their study site. Principal Investigators should consider current local public health guidance for administration of COVID-19 vaccines under EUA and marketing authorization (if any) when determining the scheduling priority of participants.

At the BD-1 visit, each participant will:

- Be encouraged to remain in the ongoing study,
- Sign a revised ICF that includes both updated safety information relevant to the ongoing study and a BD, and the option to receive a BD,
- Be given the option to receive a BD consisting of a 50 µg dose of mRNA-1273,
- Be counselled about the importance of continuing other public health measures to limit the spread of disease including social distancing, wearing a mask, and hand-washing.

After the BD-1 visit, participants who do not receive a BD will continue with the Part C Supplemental SoE for the BD-2 and BD-3 visits but will not have the BD-1a visit or the safety calls.

Participants who request a BD and are eligible and have no contraindications to further dosing will have the following study site visits and complete scheduled activities (subject to investigational vaccine availability) according to the Part C Supplemental SoE:

- BD-1 visit: Participants will receive a single 50 µg dose of mRNA-1273.
- BD-1a visit: Optional, and subject to blood sample kit availability, Day 4, 3 days after BD on Day 1.
- BD-2 visit: Day 29, 28 days after the BD on Day 1.
- BD-3 visit: Day 181, 180 days after the BD on Day 1.

The investigator is responsible for conducting all assessments as specified in the Part C Supplemental SoE, according to the schedule. As this Supplemental SoE is intended to occur in addition to the original SoEs being followed by all participants in Part B, there is a possibility for study visits to overlap. If visits overlap according to

respective visit windows, a single visit may be done with the combined study procedures completed once.

This study will be conducted in compliance with the protocol, Good Clinical Practice, and all applicable regulatory requirements.

Randomization:

In Part A, the Blinded Phase of the study, approximately 30,000 participants will be randomly assigned in 1:1 ratio to receive either mRNA-1273 100 µg or placebo. The randomization will be in a blinded manner using a centralized interactive response technology, in accordance with pre-generated randomization schedules.

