4.1.3. Part C, the Booster Dose Phase

Part C, the Booster Dose Phase providing a BD for all eligible participants who chose to receive one, is prompted by interim results of an ongoing Moderna Phase 2a study (mRNA-1273-P201), as described in [Section 4.2](#).

Each study participant will receive a notification letter and will be asked to schedule a BD-1 visit at their study site ([Table 23](#)). Principal Investigators should consider current local public health guidance for administration of COVID-19 vaccines under EUA and marketing authorization (if any) when determining the scheduling priority of participants. At the BD-1 visit, each participant will:

- Be encouraged to remain in the ongoing study,
- Sign a revised ICF that includes both updated safety information relevant to the ongoing study and a BD, and the option to receive a BD,
- Be given the option to receive a BD consisting of a 50 µg dose of mRNA-1273,
- Be counselled about the importance of continuing other public health measures to limit the spread of disease including social distancing, wearing a mask, and hand-washing.

After the BD-1 visit, participants who do not receive a BD will continue with the Part C Supplemental SoE for the BD-2 and BD-3 visits but will not have the BD-1a visit or the safety calls ([Table 23](#)).

Participants who request a BD and are eligible and have no contraindications to further dosing (see [Section 7.1](#)) will have the following study site visits and complete scheduled activities (subject to investigational vaccine availability) according to the Part C Supplemental SoE ([Table 23](#)):

- BD-1 visit: Participants will receive a single 50 µg dose of mRNA-1273.
- BD-1a visit: Optional, and subject to blood sample kit availability, Day 4, 3 days after BD on Day 1.
- BD-2 visit: Day 29, 28 days after the BD on Day 1.
- BD-3 visit: Day 181, 180 days after the BD on Day 1.

The investigator is responsible for conducting all assessments as specified in the Part C Supplemental SoE, according to the schedule. As this Supplemental SoE is intended to occur in addition to the original SoEs ([Table 16](#), [Table 17](#), [Table 18](#), and [Table 19](#)) being followed by all participants in Part B, there is a possibility for study visits to overlap. If visits overlap according to respective visit windows, a single visit may be done with the combined study procedures completed once (refer to [Table 4](#) footnotes for more detailed instructions and exceptions).

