3.5.2. Part C, the Booster Dose Phase

All participants will be asked to schedule BD-1 (BD Day 1) visit as the start of Part C, the Booster Dose Phase. Eligible participants will be provided an option to receive BD consisting of a single 50 µg dose of mRNA-1273.

After the BD 1 visit, participants who do not receive a BD will continue with the Part C schedule of events with the exception of the BD-1a (BD Day 4) visit and blood draw and the safety calls (Table 23 in the protocol).

[figure not shown]
At the BD 1 visit, participants who request a BD, are eligible and have no contraindications to further dosing (Section 7.1 in the protocol) will have subsequent study site visits and complete scheduled activities (subject to investigational vaccine availability) according to the Part C schedule of events (Table 23 in the protocol).

Figure 1 Study Flow Diagram: Part A, the Blinded Phase followed by Part B, the Open-Label Phase Including Part C, the Booster Dose Phase

Abbreviations: BD = booster dose visit; EUA = emergency use authorization

Figure 2 Part B, the Open-Label Observational Phase, and Part C, the Booster Dose Phase

- ^a All participants are encouraged to remain in the study.
- ^b All participants are given the option to be unblinded to treatment received in Part A: Blinded Phase.
- ^c All participants are counselled about the importance of continuing other public health measures to limit the spread of disease including physical-social distancing, wearing a mask, and hand-washing.
- ^d All participants sign a revised informed consent form.
- ^e All participants consent to provide a nasopharyngeal swab and a blood sample for immunologic analysis.
- ^f mRNA-1273 recipients who only received 1 dose of the mRNA-1273 vaccine will receive the second dose of mRNA-1273 vaccine.
- ^g Placebo recipients who request to receive mRNA-1273 and meet eligibility will comply with a Supplemental Schedule of Events in addition to the Original Study Schedule of Events included in the Clinical Study Protocol.
- ^h Original Study Schedule of Events are included in the Clinical Study Protocol

i Procedures required or not required based on receipt of the booster dose are clarified in the Part C Supplemental Schedule of Events included in the Clinical Study Protocol

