5.1.5. Analysis Periods

Analysis periods and treatment groups for analysis of Part B, Part C, and Primary Series are summarized in Table 1. For effectiveness, participants will be included in treatment groups based on ‘as-planned’ or ‘intent-to-treat’ assignments; for safety, participants will be included in treatment groups based on ‘as treated’ groups (treatment actually received), details are provided to Appendix F. For analysis of immunogenicity, ‘per-protocol’ sets will be used as analysis population and ‘per-protocol’ sets require participants receiving planned treatments.

Table 1 Analysis Periods for Analyses of Part B, Part C, and Primary Series

Treatment Group/Cohort	Description	Analysis Period
Part B (Effectiveness)		
mRNA-1273	Participants randomized to mRNA-1273 in the Blinded Phase Date of reference: PDV/unblinding	From PDV/unblinding to earlier date of (BD-1 visit, DBL or data cutoff date for efficacy, last observed in study ^a)
Placebo	Participants randomized to Placebo in the Blinded Phase and did not request to receive mRNA-1273 in Part B Date of reference: Dose 1 of mRNA-1273	
Placebo-mRNA-1273	Participants randomized to Placebo in the Blinded phase and requested to receive mRNA-1273 in Part B Date of reference: Dose 1 of mRNA-1273 in Part B	
Part B (Safety)		
mRNA-1273	Participants received at least one dose of mRNA-1273 in the Blinded Phase	From PDV/unblinding or 1 st dose of mRNA-1273 in Part B to earlier date of (BD- Day 1, DBL or data cutoff date for safety, last observed in study ^a).
Placebo	Participants only received Placebo in the Blinded Phase and did not receive mRNA-1273 in Part B	
Placebo-mRNA-1273	Participants only received Placebo in the Blinded phase and received mRNA-1273 in Part B	
Part C (Effectiveness, Immunogenicity, Safety)		
Booster 50 µg after mRNA-1273 primary series	Participants randomized to/received mRNA-1273 in the Blinded Phase and received booster 50 µg in Part C Date of reference: date of booster	From dose date in Part C to earlier date of (DBL or data cutoff date for safety, last observed in study ^a).

Booster 50 µg after Placebo-mRNA-1273 Primary Series	Participants randomized to /only received Placebo in the Blinded Phase and received at least one dose of mRNA-1273 in Part B and received booster 50 µg in Part C Date of reference: date of booster	

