Booster 50 µg	Participants randomized in the blinded phase and received booster 50 µg in Part C Date of reference: date of booster	From dose date in Part C to earlier date of (DBL or data cutoff date for safety, last observed in study ^a).
Not received booster	Participants randomized to/received mRNA-1273 in Part A or B and did not receive booster in Part C Date of reference: date of BD-visit 1	Up to earlier date of (DBL or data cutoff date for safety, last observed in study ^a).
Placebo	Participants randomized to/only received Placebo in Part A or B and did not receive booster in Part C Date of reference: date of BD-visit 1	From BD-visit 1 in Part C to earlier date of (DBL or data cutoff date for safety, last observed in study ^a).
Effectiveness, Immunogenicity of mRNA-1273 primary Series		
mRNA-1273	Participants randomized to mRNA-1273 in the Blinded Phase	From Dose 1 of mRNA-1273 to earlier date of (booster date, DBL or data cutoff date, last observed in study ^a).
Placebo-mRNA-1273	Participants randomized to Placebo and received mRNA-1273 in Part B	
Safety of mRNA-1273 primary Series		
mRNA-1273	Participants received mRNA-1273 in the Blinded Phase	From Dose 1 of mRNA-1273 to earlier date of (booster date, DBL or data cutoff date, last observed in study ^a).
Placebo-mRNA-1273	Participants received Placebo in the Blinded phase and received mRNA-1273 in Part B	

^a last observed in study is the earliest date of study discontinuation, study completion, or death.

All analyses will be conducted using SAS Version 9.4 or higher unless otherwise specified.

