In the Part C booster dose phase of the study, all participants will have scheduled blood sample collected at BD Day 1 visit. NP swab test at this visit is optional. Participants who received the booster dose of mRNA-1273 in Part C will have blood sample collected at BD Day 29 and BD Day 181 (6 months post-booster). For Part C, subjects with early infection, as detected by positive RT-PCR at scheduled visits, or positive bAb against SARS-CoV-2 nucleocapsid protein at the scheduled visits, will be censored at the time of early infection. If a participant had eligible symptom(s) within 14 days of positive RT-PCR at scheduled visits, the participant is considered to be a case for COVID-19.

Subjects who have no documented COVID-19 will be censored at the earlier date of DBL or data cutoff date for efficacy, date of last observed in study defined as the earlier of study completion date, early discontinuation date from study, or date of death. For analysis of Part B or primary series, subjects who have no documented COVID-19 will be censored at the earlier date of date of booster, DBL or data cutoff date for efficacy, or date of last observed in study defined as the earlier of study completion date, early discontinuation date from study, or date of death.

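### Part B effectiveness follow-up ends at the BD-1 visit in SAP Table 1 but at the booster date in Section 5.3.1.1, and the gap falls unevenly on the Placebo cohort

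*SAP*

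**What the plan says.** Both rules are in the SAP for Part B and Part C, version 2.0.

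- **Section 5.1.5, Table 1, Part B (Effectiveness):** "From PDV/unblinding to earlier date of (BD-1 visit, DBL or data cutoff date for efficacy, last observed in study".
- **Section 5.3.1.1:** one sentence covers Part B and the primary series together. It opens "For analysis of Part B or primary series, subjects who have no documented COVID-19 will be censored at the earlier date", and its list of dates makes such participants "censored at the earlier date of date of booster, DBL or data cutoff date for efficacy", or when last observed in the study. The BD-1 visit is not listed.
- **Table 1, primary series:** "From Dose 1 of mRNA-1273 to earlier date of (booster date, DBL or data cutoff date, last observed in study". Here the table and the text agree.

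BD-1 is not the same thing as receiving a booster. Section 3.5.2 says: "All participants will be asked to schedule BD-1 (BD Day 1) visit as the start of Part C, the Booster Dose Phase". Protocol Section 4.1.3 keeps decliners under observation: "participants who do not receive a BD will continue with the Part C Supplemental SoE for the BD-2 and BD-3 visits". Table 1 then gives Part C rows to people without a booster, with BD-1 as the reference date. One row is described as "Participants randomized to/received mRNA-1273 in Part A or B and did not receive booster in Part C"; the other is Placebo.

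**The concern.** A participant who attends BD-1 and declines has no booster date. Under Section 5.3.1.1 that person remains in Part B until cutoff or last observation; under Table 1 they leave at BD-1. Section 5.3.1.1 sets the censoring date only for people without an event, so under it a case after BD-1 in such a person counts in Part B. Table 1 puts the same case outside the period.

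The disputed time lies largely in the window from 1 December 2021 to cutoff, which Section 5.3.1.2.2 labels as the Omicron wave. It is also not spread evenly over the cohorts. Protocol Section 5.1.1 (criterion 8) and footnote 1 of Protocol Table 23 require at least one earlier mRNA-1273 dose for a booster. Placebo-cohort members who never had mRNA-1273 will therefore generally never have a booster date, although the Synopsis lets CDC-EUA guidance override protocol eligibility. Under the text rule nearly all time after BD-1 of Placebo attendees stays in Part B, against only the unboosted share in the vaccinated cohorts. The Part B rates would then be shown side by side over different stretches of the epidemic.

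**Working it through.** The plan gives no rate, event count or sample size for Part B effectiveness, so there is no stated figure to reproduce.

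**1. The two rules by type of participant**

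| Participant | Table 1 end | Section 5.3.1.1 end | Difference |
|---|---|---|---|
| Boosted at BD-1 | BD-1 | booster date, same day | none |
| Never attends BD-1, not boosted | cutoff or last observed | cutoff or last observed | none |
| Attends BD-1, boosted later | BD-1 | booster date | the delay |
| Attends BD-1, never boosted | BD-1 | cutoff or last observed | all time after BD-1 |

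**2. Days at stake, from dates in the documents.** The Omicron window opens on 1 December 2021 (Section 5.3.1.2.2). The cutoff is given as April 2022 without a day (Section 5.3.1.2.1), so I take 1 to 30 April. Amendment 9, which created Part C, is dated 10 September 2021.

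- Omicron-window days for an unboosted attendee with BD-1 before 1 December and followed to cutoff: 0 under Table 1; 121 (to 1 April) to 150 (to 30 April) under the text, or 0.33 to 0.41 person-years.
- All days from BD-1 to cutoff: 203 to 232 if BD-1 was on 10 September 2021; 122 to 151 if on 30 November 2021.

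**3. Illustration of the effect on a rate. None of these inputs is in the documents.** Assume 9 months from the participant decision visit to BD-1, then 5 months to cutoff, 4 of them Omicron; everyone attends BD-1; a share p is not boosted; and the Omicron rate is k times the earlier rate. Then

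rate under text / rate under Table 1 = [9 + p(1 + 4k)] / (9 + 5p)

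- p = 5%, k = 3: 9.65/9.25 = 1.04
- p = 10%, k = 5: 11.1/9.5 = 1.17
- p = 20%, k = 10: 17.2/10 = 1.72
- p = 100%, as for Placebo attendees who cannot be boosted: 22/14 = 1.57 (k = 3), 30/14 = 2.14 (k = 5), 50/14 = 3.57 (k = 10)

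At k = 5 in both cohorts, with p = 10% in a vaccinated cohort and 100% in Placebo, the rule alone multiplies the ratio of the Placebo rate to the vaccinated rate by 2.14/1.17 = 1.83.

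**4. Sensitivity to non-attendance.** People who never attend BD-1 contribute Omicron time under both rules and dilute the effect. With 20% unboosted non-attendees, p = 10% and k = 5, the Table 1 rate is (0.8×9 + 0.2×30)/(0.8×9 + 0.2×14) = 13.2/10 = 1.32 and the text rate is (0.8×11.1 + 6)/(0.8×9.5 + 2.8) = 14.88/10.4 = 1.43. The ratio falls from 1.17 to 1.08. The same step takes 1.04 to 1.02 and 1.72 to 1.28.

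**The case against.** The best reply is that Table 1 governs and Section 5.3.1.1 is loosely worded. Table 1 is the dedicated period table, Section 5.1.4 ties Part B to data collected in Part B, Section 3.5.2 makes BD-1 the start of Part C, and the Part B safety row also ends at BD-Day 1. That is the more natural reading, but it is not stated. Section 5.1.4 says only that the Table 1 periods may be used. Section 5.3.1.2 moves people out of the non-booster group when they receive the booster, and Section 5.3.1.2.1 asks for a similar approach in Part B to that of the primary series, whose follow-up ends at booster. A programmer could defend either rule.

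Other limits stand:

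- Protocol Section 9.5.1.3 makes long-term efficacy descriptive, without cohort comparison. The SAP's relative-effectiveness contrast (Section 5.3.1.2.1.1) concerns the primary series, where the dates agree. A reader might infer that a planned comparison with Placebo is biased; no such comparison is specified in Part B.
- A reader might infer that the same cases are counted twice in one analysis. They are not. The Part C Per-Protocol Set holds only boosted participants, and decliners enter through the separate booster comparison in Section 5.3.1.2.3. No analysis described in Section 5.3.1.2 uses the Part C Placebo row. Any overlap is across analyses, and the plan reuses unboosted time across analyses by design.
- Censoring for early infection at scheduled visits, withdrawal after a non-study primary series or first booster (Protocol Section 7.3.1), and rates by calendar quarter, if applied to Part B, would all lessen the effect.
- Part B results from the 4 May 2021 database lock predate BD-1 and are untouched.

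**Conclusion.** The SAP contradicts itself on when Part B effectiveness follow-up ends, and no precedence rule settles it. The difference is confined to people who attend BD-1 and are not boosted at that visit. For each one never boosted, with BD-1 before December 2021 and followed to an April 2022 cutoff, 121 to 150 Omicron-window days switch in or out of Part B; a later cutoff would add more. The text rule extends Placebo follow-up into Omicron far more than that of the vaccinated cohorts, so the descriptive rates would not be read on a like footing.

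The number of unboosted attendees by cohort is not given, so the net effect on any rate is unknown. The ratios above are illustrations and not estimates; the documents do not support taking 1.72, or any other of them, as the size of the error. The Part A result, the primary-series analysis and the Part C noninferiority tests do not depend on this choice. It should be corrected, but it does not threaten the trial's main conclusions.

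**What to change.** Split the sentence in Section 5.3.1.1.

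- **Part B:** end follow-up, for both person-time and cases, at the earliest of the BD-1 visit (boosted or not), database lock or efficacy cutoff, and last observed in study, as in Table 1. This also settles boosters given after BD-1.
- **Primary series:** keep the booster date, database lock or cutoff, and last observed.
- **Never attended BD-1:** state the Part B end date. Both current rules take these people to cutoff or last observation, so some Omicron time remains in Part B and should be visible in the tables.

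Time after BD-1 then falls outside Part B. Unboosted time still counts, properly, in the primary-series analysis and in the Not received booster group. Changing Table 1 to the booster date would also remove the contradiction, but it would keep the uneven extension of the Placebo cohort.

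The cost is a sentence or two, a programming check and some Part B person-time. For an assumed 1,000 attendees with decision visit on 15 February 2021 and BD-1 on 15 October 2021, the BD-1 rule gives 1,000 × 242/365.25 = 663 person-years. The text rule gives 686 to 770 if 5% to 20% are unboosted, so 23 to 107 person-years are given up.

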5.3.1.2. Analysis approach for effectiveness of vaccine

COVID-19 will be evaluated using incidence rates. Number of events and incidence rate will be provided in a dynamic approach for each treatment cohort, e.g., a participant without COVID-19 or SARS-COV-2 infection will no longer be considered as “at risk” in the non-booster treatment group from the timepoint when this participant received the booster dose, instead, this participant will be considered as “at risk” in the booster treatment group from that timepoint. Incidence rate will be calculated as the number of

participants with an event divided by the number of subjects at risk adjusted by person-time (years) in each treatment cohort.

5.3.1.2.1. Effectiveness of the primary series

Effectiveness of the primary series of mRNA-1273 in those vaccinated participants, will be assessed in participants initially randomized to the mRNA-1273 group (mRNA-1273, vaccinated from July-December 2020, early vaccinated) and those initially randomized to the placebo group (Placebo-mRNA-1273, vaccinated December 2020-April 2021, recent vaccinated) using the PP Primary Series Set. Part A and Part B data after Dose 1 of mRNA-1273 will be included for this analysis, and date of Dose 1 of mRNA-1273 will be used as the reference. The analysis period will be from Dose 1 of mRNA-1273 to earlier of last study participation, booster date, or data cutoff date for efficacy as presented in Table 1.

Using PP Primary Series Set, participants at risk will be those who did not have evidence of prior infection prior to Dose 1 of mRNA-1273, specifically, those in mRNA-1273 (randomized to mRNA-1273 in Part A (baseline/pre-Day 1 SARS-CoV-2 negative is required for inclusion in PP Primary Series Set), and those in Placebo-mRNA-1273 group who were SARS-CoV-2 negative at PDV/unblinding at the start of Part B.

Incidence rates will be provided over the time from Dose 1 of mRNA-1273 to receipt of booster, last study participation, or data cutoff date for efficacy. Incidence rates will also be provided by calendar quarters, as well as by the following time intervals:

- After Dose 1
 - After Dose 1 of mRNA-1273
 - After Dose 1 to before Dose 2 of mRNA-1273
 - After Dose 2 of mRNA-1273
 - Dose 2 to <14 days after Dose 2
 - ≥ 14 days after Dose 2

The last time interval “ ≥ 14 days after Dose 2” of mRNA-1273 may be further partitioned into shorter intervals. For each interval, person-time is calculated for participants at risk at

the beginning of the interval, as the time from the date of the beginning of the time interval to the date of the event/censoring for subjects with an event/censor if the event/censor occurs in the interval; or the time of the interval for subjects who continue to be at risk at the end of the interval. Incidence rate, and 95% CI for incidence rate will be calculated using the exact method adjusting for person-time will be provided by treatment cohort. Number and incidence rates of COVID-19 starting 14 days after Dose 2 of mRNA-1273 will also be provided by calendar quarters.

Incidence rate will also be provided for the periods defined by emergence and circulation of select variant of interest, e.g. December 2021- data cutoff date (Apr, 2022).

Effectiveness in Part B will be performed, and PP Set will be used with treatment cohorts listed in Table 1 for Part B analysis with similar analysis approach. For Part B, participants at risk at the start of Part B are defined as participants who did not have COVID-19 or SARS-CoV-2 infection and non-positive SARS-CoV-2 status at unblinding/PDV prior to Part B.

5.3.1.2.1.1. Relative Effectiveness of recent vaccinated vs early vaccinated (the Primary Series of mRNA-1273)

Relative effectiveness of recent vaccinated participants (Placebo-mRNA-1273) vs. early vaccinated participants (mRNA-1273) will be assessed using the reduction in incidence rate, calculated as 1- incidence rate ratio (IRR). The 95% CI of reduction in IR will be calculated using the exact method (Poisson distribution) adjusting for person-time.

The above analysis may be performed by calendar quarters and/or time periods.

